11.5.3.1.2. Secondary Efficacy Analyses

Duration of response is a key efficacy endpoint:

- Duration of response will only be evaluated in patients with an objective response of CR or PR. Patients who are alive and progression-free as of the analysis cut-off date will be censored at their last evaluable response assessment prior to initiation of any new anticancer treatment. Patients who start subsequent anticancer therapy without a prior reported progression will be censored at the last response assessments prior to initiation of the subsequent anticancer therapy.

Additional efficacy endpoints include:

- Overall response rate and DCR based on Investigator assessment will be determined (per RECIST 1.1) as described for the primary analysis of ORR based on independent central review of radiologic images (Section [11.5.3.1.1](#)).
- Progression-free survival will be estimated using the Kaplan-Meier method. Patients who die without a reported disease progression will be considered to have progressed on the date of their death. Patients who did not progress or die will be censored on the date of their last response assessment. Patients who did not have any on-study assessments and did not die will be censored on the first dosing date. Patients who started any subsequent anticancer therapy without a prior reported progression will be censored at the last response assessment prior to initiation of the subsequent anticancer therapy.
- Overall survival will be analyzed in a similar manner to PFS. In the absence of confirmation of death or for patients who are alive as of the OS cut-off date, survival time will be censored at the last known date that the patient was alive.

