5.5.1.2. Secondary Efficacy Analyses

- ORR based on Investigator assessment will be calculated and the 2-sided 95% CI will be derived by the Clopper–Pearson method. The confirmation rule of CR and PR is the same as the primary endpoint.
- DCR based on IRC and Investigator assessment will be calculated and the 2-sided 95% CI will be derived by the Clopper–Pearson method. The confirmation rule of CR and PR is the same as the primary endpoint. A minimum of a 6-week interval is required between the first dosing date and the first SD.
- PFS based on IRC and Investigator assessment will be estimated using the Kaplan–Meier method. Patients who did not progress or die will be censored on the date of their last tumor assessment. Patients who did not have any post-baseline assessments will be censored on the first dosing date. Patients who started any subsequent anti-cancer therapy without a prior reported progression will be censored at the last tumor assessment prior to initiation of the subsequent anti-cancer therapy. The censoring rule for PFS is in [Table 10](#).
- Overall survival will be estimated using the Kaplan–Meier method. In the absence of confirmation of death or for patients who are alive as of the OS cut-off date, survival time will be censored at the last known date that the patient was alive. The censoring rule for OS is in [Table 11](#).
- DOR based on IRC and Investigator assessment will be evaluated only in patients with an objective response of CR or PR. The starting time point is the first documentation of response (CR or PR). DOR will be estimated using the Kaplan–Meier method. Patients who are alive and progression-free as of the data cut-off date will be censored at their last evaluable tumor response assessment. Patients who start subsequent anticancer therapy without a prior reported progression will be censored at the last tumor assessments prior to initiation of the subsequent anticancer therapy. The censoring rule for DOR is described in [Table 12](#).

Table 10: Censoring Rules for Progression-Free Survival (PFS)

No.	Situation	End Date	Outcome
1	Documented PD between scheduled visits	Date of the first assessment that determined PD	PFS event
2	Death during the study with no prior PD	Date of death	PFS event
3	Patients still on treatment without PD as of data cut-off ^a	Date of the last tumor assessment ^b	Censored

No.	Situation	End Date	Outcome

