4	Treatment discontinuation for reasons other than PD or death, and no post baseline tumor assessments	Date of the first dose	Censored
5	Treatment discontinuation for reasons other than PD or death with post baseline tumor assessments	Date of the last tumor assessment	Censored
6	New anticancer treatment started	Date of the last tumor assessment before start of new treatment	Censored
7	Death or PD after two or more missed tumor assessments ^c	Date of the last tumor assessment before missed assessments	Censored
8	No baseline or unreadable baseline assessment but readable post baseline assessments	Date of the first dose	Censored

^a This refers to patients who were still receiving study treatment at time of data cutoff.

^b For PFS analysis, the date of last tumor assessment refers to the date of last adequate tumor assessment.

^c Two or more missed tumor assessments is defined as having either one of the following two durations being longer than 126 days (= (28 [days/cycle] x 2 [cycles] + 7 [days]) x 2):

Duration between two consecutive tumor assessments

Duration between the last tumor assessment and death or PD

Table 11: Censoring Rules for Overall Survival (OS)

No.	Situation	End Date
1	Death before cut-off	Date of death
2	Death after data cut-off	Date of data cut-off
3	Patient still alive at data cut-off	Date of data cut-off
5	Patient discontinued treatment due to any reason before data cut-off	Date last known to be alive

Table 12: Censoring Rules for Duration of Response (DOR)

No.	Situation	End Date	Outcome
1	Documented PD between scheduled visits	Date of the first assessment that determined PD	DOR event
2	Death during the study with no prior PD	Date of death	DOR event
3	Patients still on treatment without PD as of data cut-off ^a	Date of the last tumor assessment ^b	Censored
4	Treatment discontinuation for reasons other than PD or death	Date of the last tumor assessment	Censored

No.	Situation	End Date	Outcome
5	New anticancer treatment started	Date of the last tumor assessment before start of new treatment	Censored
6	Death or PD after two or more missed tumor assessments ^c	Date of the last tumor assessment before missed assessments	Censored

^a This refers to patients who were still receiving study treatment at time of data cutoff.

^b For DOR, the date of last tumor assessment refers to the date of last adequate tumor assessment.

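### The SAP's PFS text drops the protocol's exception for patients who die, and so conflicts with its own Table 10 on deaths before any scan

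*SAP*

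**What the plan says.** **Protocol.** Section 11.5.3.1.2 (Cohorts A and B) states: "Patients who did not have any on-study assessments and did not die will be censored on the first dosing date". Section 11.5.3.2.2 gives Cohort C the same rule. Both sections also treat death without reported progression as progression on the date of death. Amendment 1 of the protocol has the same two rules.

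**SAP text.** The PFS bullet in 5.5.1.2 first says: "Patients who did not progress or die will be censored on the date of their last tumor assessment". It then says: "Patients who did not have any post-baseline assessments will be censored on the first dosing date". The condition about not having died is gone, and so is the sentence making death without progression an event. The bullet ends by naming Table 10 as the place where the PFS censoring rule is found. The Cohort C bullet in 5.5.2.2 has the same omission and the same reference to Table 10.

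**SAP Table 10.** Row 2, "Death during the study with no prior PD", is a PFS event on the date of death, with no requirement for a scan. Row 4, "Treatment discontinuation for reasons other than PD or death, and no post baseline tumor assessments", is censored at the first dose. Row 6 censors at the last assessment before new anticancer treatment. Row 7, "Death or PD after two or more missed tumor assessments", is censored at the last assessment before the gap.

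**Elsewhere in the SAP.** Tables 8 and 13 define PFS with death from any cause as an event. Section 6 declares no changes to the planned analyses.

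**The concern.** Patients who die before a first scan have the shortest PFS times. Censoring them at time zero removes them from the risk set before they can count, and that censoring is informative, so the estimated curve can only move up. The populations are previously treated patients with advanced disease, for whom some early deaths are plausible.

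A programmer working from the text could read the omission as deliberate. The RFS bullet in SAP 5.5.2.2 keeps the corresponding sentence, that death without relapse counts as relapse on the date of death, while the PFS bullets do not. No reason for the difference is given.

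**Working it through.** No sample size, power or alpha rests on PFS, so there is no planned figure to reproduce. The check compares the rules and then sizes the consequence.

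**1. Rules side by side, for a patient with no post-baseline scan**

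| Case | Protocol | SAP text | SAP Table 10 |
|---|---|---|---|
| Alive, stopped for another reason | Censored at first dose | Censored at first dose | Row 4: censored at first dose |
| Dies on treatment | Event at death | Censored at first dose | Row 2: event at death |
| Stops for another reason, then dies | Event at death | Censored at first dose | Row 2 (event) and row 4 (censored) both fit |

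The protocol and the SAP text differ in the last two cases. The table agrees with the protocol in the second and is undecided in the third. The third row assumes that no new anticancer therapy was started.

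**2. Does row 7 catch these deaths?** The gap is (28 × 2 + 7) × 2 = 126 days, which matches the SAP. The first scan is due at 28 × 2 + 7 = 63 days at the latest. Baseline imaging may be up to 28 days before first dose, so a death before the first scan is due falls at most 63 + 28 = 91 days after the baseline scan. That is under 126, so row 7 does not apply. It could apply to an unscanned patient who dies more than 126 days after baseline imaging.

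**3. Can the undecided case occur?** Protocol Table 1 asks for an end-of-treatment scan only if the previous one was at least 9 weeks (63 days) earlier. With baseline imaging up to 28 days before first dose, an end-of-treatment visit less than 63 − 28 = 35 days after first dose never requires one. Such a patient, dying before the next scheduled scan, has no post-baseline assessment.

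**4. Size of the bias.** Take N patients, of whom k die unscanned, and let d = k/N. Suppose there is no other early censoring. At a time t after those k deaths, with E events in total:

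- deaths counted as events: S(t) = (N − E)/N
- deaths censored on Day 1: S*(t) = ((N − k) − (E − k))/(N − k) = S(t)/(1 − d)

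The factor is 1/0.95 = 1.053, 1/0.90 = 1.111 and 1/0.85 = 1.176 for d = 5%, 10% and 15%. With an assumed 6-month PFS of 30%, S* is 31.6%, 33.3% and 35.3%.

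For the median, let the remaining patients be exponential with an assumed median of 4 months. Counting the deaths gives 4 × log2(2(1 − d)) = 3.70, 3.39 and 3.06 months, against 4.0 under Day-1 censoring.

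**5. Per patient.** One patient censored this way multiplies later estimates by N/(N − 1). At the protocol's planned sizes that is 100/99 = 1.010 in Cohort A, 35/34 = 1.029 in Cohort B and 20/19 = 1.053 in Cohort C.

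**The case against.** The strongest reply is that the SAP already has the right rule. The bullet points to Table 10 for PFS censoring. Row 2 makes death without progression an event, and row 4 limits first-dose censoring to patients who stopped for reasons other than progression or death. The preceding sentence concerns patients who neither progressed nor died, so the disputed sentence may be read as continuing with that group. The endpoint definitions include death from any cause, and section 6 disclaims any change.

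Most of this stands. A reader might infer from the text that every patient who dies before a scan will be censored on Day 1. The documents do not support that: for deaths on treatment the cited table gives the protocol's answer. The 1/(1−d) figures therefore illustrate the literal sentence, not what the plan as a whole prescribes. They hold only after all such deaths have occurred, with a smaller ratio before then.

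The reply does not remove the conflict. The sentence is unqualified in two sections and disagrees with the table beside it. Row 4 turns on the reason for stopping treatment, so a later death does not take the patient out of it. Where rows 2 and 4 both fit, the table gives no order and the text points to Day-1 censoring.

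**Conclusion.** The point holds as a text–table conflict with one unresolved case, and it is minor. The SAP sentence contradicts the protocol and Table 10 row 2. The practical exposure is twofold: someone may program from the text, and a patient who stops for another reason unscanned and then dies has two possible outcomes.

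The direction of the bias is certain (PFS too high); its size is not. It depends on the fraction of patients affected, which the documents do not give. The range of 1.05 to 1.18 rests on an assumed 5% to 15% and on no other early censoring. If only the undecided case is mishandled, the same formula applies with the smaller fraction of such patients.

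PFS is an additional secondary endpoint in Cohorts A and B and a secondary endpoint in Cohort C, with no hypothesis test attached. The primary ORR and CR-rate analyses use the All Treated Population, so a patient who dies unscanned stays in the denominator as a non-responder.

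**What to change.** In SAP 5.5.1.2 and 5.5.2.2, replace the sentence with wording to this effect: *A patient with no post-baseline assessment who has not died is censored on the first dosing date. A death without prior PD is an event on the date of death, subject to rows 6 and 7 of Table 10.*

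Add a note to Table 10 that row 2 takes precedence over row 4. Confine the note to row 4. A general rule that event rows override censoring rows would empty row 7, since every case in it is also a death or a progression. It would also override row 6, against the protocol's censoring at the start of new anticancer therapy. Row 5 overlaps with row 2 in a similar way for patients who do have a post-baseline scan; that is a separate question, but it can be looked at in the same revision.

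The cost is a reworded sentence in two SAP sections and one table note. It needs no new data and changes no sample size, power or alpha.

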^c Two or more missed tumor assessments is defined as having either one of the following two durations being longer than 126 days (= (28 [days/cycle] x 2 [cycles] + 7 [days]) x 2):

Duration between two consecutive tumor assessments

Duration between the last tumor assessment and death or PD

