6. CHANGES IN PLANNED ANALYSIS

There have been no changes to the initially planned analyses as of the finalization of this SAP.

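### For PFS and DOR, the SAP both counts and censors a death more than 126 days after the last scan, against the protocol's event rule, and its gap footnote literally also reaches gaps that clean scans had closed

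*SAP*

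**What the plan says.** **Protocol.** Table 4 defines PFS to death from any cause or progression, and the key secondary DOR to progression or death from any cause. Section 11.5.3.1.2 adds for PFS: "Patients who die without a reported disease progression will be considered to have progressed on the date of their death". The same section censors patients without an event, and patients who start new anticancer therapy without prior PD. It has no rule on missed scans.

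**SAP, Section 5.5.1.2.** Row 2 of Table 10 (PFS) and of Table 12 (DOR) makes a death with no earlier PD an event on the date of death, without any limit on the time since the last scan. Row 7 of Table 10 and row 6 of Table 12 censor "Death or PD after two or more missed tumor assessments", with the end date set to "Date of the last tumor assessment before missed assessments". Footnote c of each table reads: "Two or more missed tumor assessments is defined as having either one of the following two durations being longer than 126 days". The two durations are "Duration between two consecutive tumor assessments" and "Duration between the last tumor assessment and death or PD".

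**SAP, Section 6.** "There have been no changes to the initially planned analyses as of the finalization of this SAP".

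**The concern.** There are two defects in one rule.

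First, a patient who dies more than 126 days after the last scan, with no PD and no new therapy, is an event under the protocol and under row 2 of the SAP tables, and a censoring under the gap row. No precedence is stated, so two programmers could code the same patient differently, and a reader of Section 6 would not know that the event definition had been narrowed.

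Second, the first duration in footnote c is not tied to the interval before the event. Taken literally, it reaches back to a gap that later clean scans had closed, and discards both the documented progression-free time and the PD itself.

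At stake are the PFS curve and DOR, which the protocol names as its key secondary endpoint. Gaps are plausible here. Protocol Section 6.3 relaxes scan timing during the pandemic, and Section 8.1.1 lets a patient stop treatment for symptomatic deterioration without radiologic PD. If such patients also stop scanning and then die, censoring them is informative. The responder sets are small: at the target rates, 25% of 100 is 25 responders in Cohort A and 35% of 35 is about 12 in Cohort B, so one reclassified patient is about 4% or 8% of the DOR set.

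**Working it through.** **1. The plan's own figure.** (28 x 2 + 7) x 2 = 63 x 2 = 126 days, as stated. With scans 56 days apart and a window of 7 days either side, one missed scan gives a gap of 112 ± 14 = 98 to 126 days, and two missed scans give 168 ± 14 = 154 to 182 days. The threshold does separate one missed scan from two. The number is sound; the fault lies in where it is applied.

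**2. Two scan histories** (days from first dose, baseline scan taken as day 0, no new therapy):

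| History | Gaps (days) | Protocol | SAP gap row, literal | SAP, second duration only |
|---|---|---|---|---|
| Open gap: clean scans 56, 112; death 250 | 56, 56, 138 | Event, day 250 | Censored, day 112 | Censored, day 112 |
| Closed gap: clean scans 56, 112, 280, 336; PD 392 | 56, 56, 168, 56, 56 | Event, day 392 | Censored, day 112 | Event, day 392 |

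In the open-gap history, SAP row 2 also gives an event at day 250, so the SAP contains both answers. In the closed-gap history, a patient with the same scans but no PD would be censored at the last scan, day 336 (Table 10 rows 3 and 5). Under the literal reading, observing the PD therefore removes 336 − 112 = 224 days of documented progression-free time. Whether the patient is censored early then depends on the later outcome.

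**3. Size when missingness is unrelated to outcome.** The documents give neither a missed-scan rate nor a PFS median. Assumed: exponential time to event with median 120 or 240 days, 25% of events deaths, scans every 56 ± 7 days, each missed independently, cut-off at 2 years, 20,000 simulated patients per setting.

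| True median | Scans missed | Events censored, second duration only | Events censored, literal footnote | KM median: protocol / second duration only / literal |
|---|---|---|---|---|
| 120 | 5% | 0.5% | 0.8% | 160 / 157 / 156 |
| 120 | 10% | 1.7% | 2.7% | 162 / 161 / 161 |
| 120 | 20% | 6.2% | 9.7% | 165 / 163 / 162 |
| 240 | 5% | 0.5% | 1.1% | 274 / 274 / 274 |
| 240 | 10% | 1.9% | 3.9% | 277 / 277 / 276 |
| 240 | 20% | 6.5% | 13.2% | 278 / 280 / 276 |

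The largest shift is 160 − 156 = 4 days.

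**4. Size when late deaths or closed gaps are imposed.** Assumed: exponential PFS with median 6 months and 8-week scans.

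- Late deaths in 10% of patients (126 days plus a mean of 60 after the last scan; 25% of events deaths). PFS under the protocol rule against the gap rule: 0.680 and 0.671 at 4 months, 0.553 and 0.549 at 6, 0.430 and 0.441 at 9, 0.294 and 0.308 at 12. The differences are −0.9, −0.4, +1.1 and +1.4 points.
- A separate run with 5, 10 and 15% late deaths, at 12 months: 0.296 to 0.302, 0.297 to 0.309 and 0.310 to 0.331, that is +0.6, +1.2 and +2.1 points.
- Closed gaps assigned to 10 or 20% of patients, literal footnote, at 9 months: 0.430 to 0.409 and 0.423 to 0.377, that is −2.1 and −4.6 points.

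For scale, the standard error of a 30% proportion without censoring is √(0.30 x 0.70 / 100) = 4.6 points in Cohort A and √(0.30 x 0.70 / 35) = 7.7 points in Cohort B.

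**The case against.** The strongest reply has four parts.

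- **The conflict is narrow.** Scans continue every 8 weeks until PD or new therapy, and the protocol itself censors patients who start new therapy without prior PD. Only deaths with no PD, no new therapy and no scan for more than 126 days are in dispute. This stands. A reader might infer that the protocol counts every death without PD as an event; its own new-therapy rule says otherwise. For DOR the conflict rests on the endpoint definition, since the sentence on deaths is written for PFS.
- **Footnote c can be read narrowly.** If the PD scan is itself the last assessment, the second duration is zero for PD, and the first is needed to catch the gap just before the PD scan. On that reading closed gaps are safe. The reading is possible, and it may be what was meant, but the text does not limit the first duration to that interval.
- **The effect is small and the endpoints are descriptive.** PFS and DOR are single-arm Kaplan-Meier summaries, and no comparison is tested on them. The rule needs two consecutive missed scans, so the larger assumed rates in step 4 are demanding. This stands and limits the weight of the point.
- **The protocol leaves detail to the SAP, and the choice of main handling is partly judgement.** That is fair, particularly for PD found after a gap. It does not cover an unlisted reversal of an event that the protocol counts, nor two contradictory rows in one table. The age of the SAP does not explain it: Amendment 1 carries the same sentence on deaths.

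**Conclusion.** The rule is wrong as written, on two counts: the gap row contradicts row 2 and the protocol on deaths without PD or new therapy, undeclared in Section 6; and footnote c, taken literally, censors a documented PD before a closed gap.

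A reader might infer that the rule inflates PFS and DOR. The documents do not support that as a general statement. They give no missed-scan rate, late-death rate or PFS median. Under the assumptions in step 4 the late-death effect is negative at 4 and 6 months and positive at 9 and 12, and the closed-gap effect runs downward. The late-death differences are below one standard error for either cohort. If missingness is non-informative, medians barely move; if patients stop scanning because they are deteriorating, the effect is larger by an amount the documents cannot settle. The closed-gap effect also holds only under the literal reading.

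**What to change.** 1. Make the main PFS and DOR analyses follow the protocol: death without PD or new anticancer therapy, and documented PD, are events on their own dates. State which row prevails when row 2 and the gap row both apply.
2. Reword footnote c so that it covers only the interval between the last adequate assessment and the PD scan or death that immediately follows it. This settles the meaning whichever reading was intended.
3. Report missed-assessment censoring, with the reworded footnote, as a sensitivity analysis, and record it in SAP Section 6.
4. Carry the correction into Cohort C, where PFS uses Table 10, DOR uses Table 12, and Tables 15 to 17 repeat the two-duration footnote.

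The cost is SAP wording and one extra Kaplan-Meier run per endpoint. No data collection changes.

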5.5.1. Cohorts A and B

The description of each efficacy endpoint for Cohorts A and B is provided in [Table 8](#).

Table 8: Efficacy Endpoint Definitions for Cohorts A and B

Endpoint	Definition
ORR	The proportion of patients experiencing a best overall response of PR or CR (per RECIST 1.1), based on IRC and Investigator assessment
DCR	The proportion of patients experiencing a best overall response of SD, PR, or CR (per RECIST 1.1), based on IRC and Investigator assessment
DOR	The time from the first documentation of response (CR or PR per RECIST 1.1 based on IRC and Investigator assessment) to the first documentation of objective tumor progression or death due to any cause, whichever occurs first
PFS	The time from first dose of study therapy to the date of death (any cause) or disease progression (based on IRC and Investigator assessment), whichever occurs first
OS	The time from the date of first dose to the death date

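### SAP Table 10 rows 2 and 8 give opposite PFS outcomes for a patient with no readable baseline, readable later assessments and a death without prior progression, and no order of precedence is stated

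*SAP*

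**What the plan says.** SAP Table 8 defines PFS as "The time from first dose of study therapy to the date of death (any cause) or disease progression". Four kinds of row in SAP Table 10 (section 5.5.1.2) matter here.

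- Row 2: "Death during the study with no prior PD" is a PFS event on the date of death.
- Rows 4 and 5 are censoring rows that exclude deaths in words. Row 4 reads "Treatment discontinuation for reasons other than PD or death, and no post baseline tumor assessments" and censors at first dose.
- Row 7: "Death or PD after two or more missed tumor assessments" is censored, so this row names death and overrides it.
- Row 8: "No baseline or unreadable baseline assessment but readable post baseline assessments" has the end date "Date of the first dose" and the outcome censored. Death is neither mentioned nor excluded.

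Neither the table nor the text around it ranks the rows. SAP 5.5.2.2 uses Table 10 for Cohort C PFS as well. For EFS, Table 17 repeats the pair for patients without a CR: row 8 makes death without prior PD an event, and row 14 carries the same no-baseline situation with censoring at first dose.

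Protocol 11.5.3.1.2 states: "Patients who die without a reported disease progression will be considered to have progressed on the date of their death". Its only first-dose censoring rule is: "Patients who did not have any on-study assessments and did not die will be censored on the first dosing date". Protocol 11.5.3.2.2 uses the same wording for Cohort C PFS. The protocol has no censoring rule for a missing or unreadable baseline.

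**The concern.** A missing baseline prevents progression from being measured against it, but it does not make a death unobservable. If a programmer lets row 8 prevail, the patient leaves the risk set at time zero and the death drops out of PFS, while the same patient stays in the All Treated denominator for ORR. If row 2 prevails, the death counts. The SAP supports either coding, so the choice would be made at programming, in an open-label study where outcomes are already visible. SAP section 6 declares no changes to the planned analyses, so nothing tells the reader that the protocol's event definition might not be followed for these patients.

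**Working it through.** **Does one patient meet both rows?** Take a patient with an unreadable baseline scan, readable later scans and no PD, who then dies without new therapy or missed assessments.

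- Row 2 needs death and no prior PD. Both hold, so the outcome is an event at death.
- Row 8 needs no readable baseline and readable later assessments. Both hold, so the outcome is censored at first dose.

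The patient meets both rows, with opposite outcomes.

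**Does the table settle the order?** Two features point in different directions.

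- Row 7 names death when it overrides it and row 8 does not, which favours row 2.
- Rows 4 and 5 exclude death and row 8 does not. Row 8 also works only by displacing other rows: without it, a living patient of this kind would be censored at the last assessment, under row 3 if on treatment or row 5 if off treatment. A row that must displace rows 3 and 5 can reasonably be read as displacing row 2 too.

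**Which coding agrees with the governing definitions?** SAP Table 8 and protocol 11.5.3.1.2 both count the death. The protocol's first-dose rule fails on two counts for this patient, who has on-study assessments and has died. Only row 2 agrees. The SAP text above Table 10 gives no extra protection, because its version of the protocol's first-dose rule leaves out the condition that the patient did not die (row 4 of the table keeps it).

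**EFS.** The text of protocol 11.5.3.2.2 and SAP 5.5.2.2 counts death as an event and censors only patients with none of the EFS events. Table 17 rows 8 and 14 overlap as above, within the leukemia-presentation patients who have no CR.

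**Size (illustration).** The plan states no figure to reproduce. Assumptions: k affected patients, all dying before a landmark at which about half the cohort is event-free, with no other censoring before it. Let s be the number event-free at the landmark. The Kaplan–Meier estimate is then s/n under row 2 and s/(n − k) under row 8. The values of n are the cohort sizes in protocol 11.1.

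| n | s | Row 2 | Row 8, k = 1 | Row 8, k = 2 | Row 8, k = 5 |
|---|---|---|---|---|---|
| 100 (A) | 50 | 50/100 = 50.0% | 50/99 = 50.5% | 50/98 = 51.0% | 50/95 = 52.6% |
| 35 (B) | 17 | 17/35 = 48.6% | 17/34 = 50.0% | 17/33 = 51.5% | 17/30 = 56.7% |
| 20 (C) | 10 | 10/20 = 50.0% | 10/19 = 52.6% | 10/18 = 55.6% | 10/15 = 66.7% |

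Each affected patient also removes one event. The direction of the curve depends on when the patient dies. If the one patient among 100 dies after the landmark, row 8 gives 49/99 = 49.5%, slightly below 50.0%.

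**The case against.** A reader might infer that the SAP orders deaths to be censored for any patient without a readable baseline. The documents do not support that. Row 8 also requires readable later assessments, so a patient with no scans at all who dies falls under row 2. Nor does row 8 say that it overrides a death, as row 7 does. Reading row 2 as governing is at least as natural, and the defect is an unresolved overlap.

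Nor does it follow that every affected death would be lost because of row 8. A death after new anticancer therapy or after two or more missed assessments is censored by rows 6 and 7 in any case. It also goes too far to call the row a hidden exclusion. It is printed in the SAP, the protocol defers detailed methods to the SAP, and the deaths still count in OS.

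Cases should be rare. Cohorts A and B require measurable disease at entry, without waivers, so the likely route is a baseline that the central reader cannot read. That route does not carry over to Cohort C, where investigators assess response from marrow, blood, imaging and clinical findings, with adjudication.

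The last objection is that excepting deaths makes time at risk depend on outcome: affected patients who die contribute time and an event, while survivors contribute neither. That is true, but the protocol already accepts the same convention for patients with no on-study assessments. These arguments limit the point; they do not remove the overlap.

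**Conclusion.** The overlap is real and minor. Table 10 rows 2 and 8 conflict for one definable kind of patient, no precedence is given, and only the row 2 outcome agrees with the protocol and the SAP's PFS definition. Table 17 rows 8 and 14 share the problem for EFS in leukemia-presentation patients without a CR, a subset of about 20 Cohort C patients whose size the documents do not give. Only secondary endpoints are involved.

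The documents give no rate of missing or unreadable baselines, so the values of k are assumptions. On the stated assumptions, one such death moves a landmark PFS estimate by about 0.5 points in Cohort A, 1.4 in Cohort B and 2.6 in Cohort C. The event count can only fall if row 8 is applied; the direction of the curve is not fixed.

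**What to change.** In SAP Table 10 row 8 and Table 17 row 14, add *and no death on study* to the situation. Add a note that a death with no prior PD remains an event on the date of death (Table 10 row 2; Table 17 row 8), subject to the existing rules on new anticancer therapy and missed assessments (Table 10 rows 6 and 7; Table 17 rows 12 and 13). The note needs both limits: without the no-prior-PD condition and the missed-assessment rule, it would create a new conflict with Table 10 row 7 and Table 17 row 13.

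The cost is a few words in two tables, with no new data and no effect on sample size or the primary analyses. The statistical price is that affected patients who die contribute time and an event while survivors are censored on Day 1, which matches the protocol's existing first-dose convention. The change should be made before the analysis is programmed.
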